1.2 Background

The InterGraft™ Venous Anastomotic Connector was developed for minimally invasive venous anastomoses of a standard hemodialysis graft. The current study will evaluate the safety and performance of the InterGraft™ Venous Anastomotic Connector for a venous anastomosis of a commercially available, 6 mm diameter, ePTFE hemodialysis graft. While recognizing that a native fistula is the recommended access for hemodialysis, AV grafts remain a frequently used access type. This study focuses on subjects who have a failed fistula, cannot have a fistula or are better suited for an AV graft, as determined by the physician. The graft implant procedural outcomes, the number and type of major adverse events, and patency throughout a six (6) month follow-up period will be evaluated. The 6-month patency rate will be compared with a pre-specified patency performance goal that is drawn from prior surgical AV graft literature and published performance standards.^(10, 14-20 in the Investigational Plan)

1.3 Device Description

[figure not shown]
The InterGraft™ Venous Anastomotic Connector (VIG) is designed for transcatheter delivery within a vein and connection to a graft that has been tunneled under the skin in a standard manner. The connections are made via small skin incisions.

The InterGraft™ VIG is constructed with a nitinol framework encapsulated with ePTFE in the midsection and uncoated at the ends (**Figure 1**). The InterGraft™ VIG is delivered and deployed within the target vessels using customized transcatheter delivery systems. The VIG is a flexible, flared, self-expanding endoprosthesis designed for coaxial placement in peripheral veins up to 10 mm in diameter. The distal flared end is configured as a nitinol scaffold with anchoring barbs that extend into the vein wall. The ‘graft end’ of the VIG is configured as a stent-like framework for anchoring within the ePTFE graft. The

materials used in constructing the VIG are all medical-grade with well-established biocompatibility profiles.

The VIG is supplied pre-mounted in customized percutaneous delivery systems for over-the-wire delivery via a 11F sheath. The VIG is intended as a permanent implant. The delivery systems is a sterile, single use, disposable item.

Figure 1- InterGraft Venous Anastomotic Connector (VIG). Note barbs that anchor VIG within the vein (arrows).

2.0 STUDY DESIGN

This is a multicenter, prospective, non-randomized design study. The planned study enrollment is 146 evaluable subjects who require AV graft placement for hemodialysis and who meet the entry criteria.

The current study will allow for a maximum enrollment of 173 subjects, including a provision for 12 subjects lost to follow-up and up to 15 roll-in cases. Data from roll-in subjects will not be included in the primary analysis but will be analyzed separately.

The study will include up to 23 participating clinical centers. Study site investigators will be physicians skilled in AVG placement and interventional techniques. Study data will be collected up to the point at which each subject has completed the 6-month endpoint or experienced a terminal study endpoint.

No single clinical site may contribute more than 25% of the total enrollment (excluding roll-in subjects).

2.1 Study Objectives

The study has the following primary objective:

Primary: To demonstrate that the 6-month cumulative patency of grafts connected with the InterGraft™ VIG is similar to that of grafts connected using standard sutured anastomoses.

2.2 Study Endpoints and Hypotheses

2.2.1 Primary Endpoint

The primary endpoint is cumulative patency at 6 months, defined as the percentage of subjects free from loss of access of the study graft for hemodialysis, assessed at 6 months.

The primary study endpoint of the cumulative patency rate at 6 months will be evaluated in the following testable hypotheses:

$$H_0: (\text{Cumulative Patency Rate})_{6 \text{ Months}} \leq \text{PG}$$

$$H_1: (\text{Cumulative Patency Rate})_{6 \text{ Months}} > \text{PG}$$

Where, PG = Performance Goal, here equal to 75%.

2.2.1.1 Choice of Performance Goal

Based on a review of the literature and prior studies of similar AVGs cleared for commercial distribution, the observed cumulative patency rate at 6 months for standard AV graft implants ranged from 65% to 98%. Based on the proposed sample size for the current study (see below) and an expected cumulative patency rate of 84.6% seen for AVGs placed using the VIG in the initial phase, the exact, lower two-sided 95% confidence bound for cumulative patency is estimated to be 79.9%. A comparison to a target Performance Goal (PG) of 75% has been chosen for the evaluation.

2.2.2 Secondary Endpoints

Secondary endpoints for the study include:

1. Acute device success, defined as AV graft flow at the end of the procedure (determined by palpable graft thrill and audible bruit), without significant bleeding or emergent surgery
2. Primary Unassisted Patency at 6 Months, defined as the percentage of subjects free from the first occurrence of either access thrombosis or an access procedure performed to maintain access patency.
3. Time to First Cannulation, defined as the time from initial access placement to the first graft cannulation.
4. Number and type of interventions required to maintain secondary patency
5. Number and type of serious adverse events (SAEs) through 6 months. SAEs include the following: death, emergent surgery, infection requiring treatment (e.g., prolonged or intravenous antibiotic therapy), significant bleeding (defined as bleeding requiring treatment), and pseudoaneurysm.

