8.0 STUDY ENDPOINTS

Primary Endpoint

The primary endpoint is cumulative patency at 6 months, defined as the percentage of subjects free from loss of access of the study graft for hemodialysis, assessed at 6 months.

Secondary Endpoints

Secondary endpoints for the study include:

1. Acute device success, defined as AV graft flow at the end of the procedure as determined by palpable graft thrill and/or audible bruit, without significant bleeding or emergent surgery.
Primary Unassisted Patency at 6 Months, defined as the percentage of subjects free from the first occurrence of either access thrombosis or an access procedure performed to maintain access patency.
2. Time to First Cannulation, defined as the time from initial access placement to the first graft cannulation.
3. Number and type of interventions required to maintain secondary patency
4. Number and type of serious adverse events (SAEs) through 6 months. SAEs include the following: death, emergent surgery, infection requiring treatment (e.g., prolonged or intravenous antibiotic therapy), significant bleeding (defined as bleeding requiring treatment), and pseudoaneurysm.

Expected interventions for restoration of patency will be documented and reported separately, are reflected in the evaluation of cumulative patency, and will not be tabulated again as SAEs.

Endpoints will be evaluated acutely (at the time of implant), at time of any AVG intervention, at two weeks, and monthly through 6 months for all subjects. The study AVG patency evaluation starts immediately after the index procedure is completed (e.g., subject leaves the surgery suite). This means that once the AVG is created, patency evaluation begins. The occurrence of acute thrombus and treatment thereof during the index procedure while the vascular access is being created does not trigger the loss of primary patency.

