The occurrence of AEs, including SAEs and UAEs, will be monitored throughout the study duration. Adverse event information will be collected and reported on designated AE forms, assessed and classified by the principal investigator as serious/not serious. The investigator will also determine the relatedness of the AE to the study device and study procedure according to the following definitions:

- Related (AE is clearly related to the device/procedure);
- Possibly related (AE may be related to the device/procedure);
- Unrelated (AE is clearly not related to the device/procedure).

Procedure-related AEs are AEs that occur during the time interval from when the subject enters and leaves the surgical treatment suite for the index procedure (e.g., AVG implant procedure). Thus, the procedure includes use of the study device, as well as any treatments or procedures that are applied before or after the study device (eg, anesthesia, suturing of incision sites after AVG is completed), while the subject is in the surgical suite.

Device-related AEs are AEs related or possibly related to the study device or to the study device procedure which includes delivery, deployment, and attachment of the study device to the AVG.

Device-related events that occur during the study procedure are also procedure-related events.

Procedure-related events may not necessarily be related to the study device; for example, a procedure event such as an anesthesia reaction would not be related to the study device.

Device-related events may also occur after the study procedure, for example, fracture of metal strut in the VIG.

For situations in which a study subject has a serious adverse event (SAE) that results in abandonment of the study AV access site, the subject should be followed to the next follow-up visit after the study AVG is abandoned. This is done in order to collect general information about the subject's health status after the AVG is abandoned.

After that visit, the subject can then be formally withdrawn from the study. This means that the date that AVG patency is lost and the date of study withdrawal are not necessarily the same date.

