The following final events will justify cessation of study follow-up: death, AVG abandonment, lost to follow up (at least 3 attempts to contact the subject should be made and documented), or completion of study follow-up.

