4.4 Secondary Endpoints

The following secondary endpoints will be evaluated in the study, but there are no formal hypotheses that are tested or associated significance levels assigned to results. Nominal confidence intervals may be calculated in summarizing clinical results for secondary endpoints but not for purposes of product labeling.

1. Acute device success will be summarized by the success rate and associated 95% confidence interval.
2. Primary Unassisted Patency at 6 Months will be summarized by the patency rate and associated 95% confidence interval.
3. Time-to-First-Cannulation will be summarized by the median time and frequency distribution.
4. Number and type of interventions required to maintain secondary patency will be summarized by the frequency distributions of numbers and types of interventions.
5. Number and type of serious adverse events (SAEs) will be summarized by frequency distributions of the numbers and types of SAEs, the subject rates of SAEs by type, and the proportion of subjects with at least one SAE.

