4.9 Sensitivity Analyses

The primary endpoint is cumulative patency at 6 months, defined as the percentage of subjects free from loss of access of the study graft for hemodialysis, assessed at 6 months. Loss of access, including graft abandonment, and the associated time of occurrence will be considered events for purposes of the primary endpoint analysis.

Subjects who have died for reasons unrelated to the study device will be considered as censored with regard to the primary endpoint analysis at the time of death, and their last known status will be used.

Subjects who have become lost to follow-up or who have withdrawn consent for participation in the study prior to 6 months will be considered to have missing primary endpoint outcomes. In the primary analysis, these subjects will be considered to have been censored at the last documented determination of their status prior to study exit. Sensitivity analyses will also be performed to determine the potential impact of these missing data on the primary analysis results, including a tipping point analysis where their status at the time of study exit is assumed to be loss of patency.

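### Primary unassisted patency has no failure event for a graft removed or abandoned without thrombosis or a patency procedure, so any such loss would bias the rate upward.

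*SAP*

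**What the plan says.** Protocol 8.0 and SAP 2.2.2 give the same definition. The protocol has "Primary Unassisted Patency at 6 Months, defined as the percentage of subjects free from the first occurrence of either access thrombosis", and both documents continue to the same second event, so a subject counts as patent when "free from the first occurrence of either access thrombosis or an access procedure performed to maintain access patency". The word joining the two events closes the list.

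On analysis, SAP 4.4 says only that "Primary Unassisted Patency at 6 Months will be summarized by the patency rate and associated 95% confidence interval", and Protocol 18.0 (Secondary Endpoints) says the same. Neither names an estimator, lists events or gives a censoring rule for this endpoint.

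Abandonment appears in three other places:
- SAP 4.9, for the primary endpoint: "Loss of access, including graft abandonment, and the associated time of occurrence will be considered events for purposes of the primary endpoint analysis".
- SAP 3.2, on stopping follow-up: "The following final events will justify cessation of study follow-up: death, AVG abandonment, lost to follow up". Protocol 11.0 (Final Events) agrees.
- Protocol 21.0, on what to do after "a serious adverse event (SAE) that results in abandonment of the study AV access site". The subject is seen at one more visit, and the protocol notes that the date patency was lost may differ from the withdrawal date.

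The serious adverse events listed in SAP 2.2.2 include infection requiring treatment and "significant bleeding (defined as bleeding requiring treatment), and pseudoaneurysm".

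**The concern.** By the usual convention, a graft that can no longer be used is not patent with or without assistance, so unassisted patency cannot exceed cumulative patency for any individual subject. The two-event definition breaks that nesting. Excising or abandoning a graft that has not clotted is not thrombosis, and it is not a procedure to maintain patency. The same subject can therefore fail cumulative patency and remain free of failure on unassisted patency.

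Two things are at stake. The reported unassisted rate would omit some complete graft losses. The difference between the two patency rates, which a reader would take as the share of grafts kept going by intervention, would shrink by the same number of subjects. Because no handling rule is stated, the same data could also be scored as success, censored or failed after results are known. This is a single-arm study meant to support a 510(k), so there is no concurrent control in which the same scoring would cancel out.

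**Working it through.** **The plan's own figure.** The documents state no expected value for primary unassisted patency, so there is none to reproduce. The sample size used as denominator does hold up. With an exact binomial test, one-sided alpha 0.025, performance goal 75% and expected rate 84.6% (SAP 2.3), n = 146 needs at least 120 patent grafts. The exact alpha is 0.0249 and the power is 82.3%, against the stated 80%.

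**Tracing one subject through the text.** Take a graft excised for infection in month 2 that had never clotted and had no earlier procedure.
1. Cumulative patency (SAP 4.9): loss of access, so an event at the date of excision.
2. Unassisted patency (SAP 2.2.2): no thrombosis and no procedure to maintain patency, so no event.
3. After excision, follow-up may stop (SAP 3.2). The subject is then counted as free at 6 months (simple proportion) or censored (Kaplan-Meier). SAP 4.4 does not say which.

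**Inputs for the size.** N = 146 evaluable or 158 enrolled (SAP 2.3). Let k be the number of grafts lost this way with no earlier thrombosis or patency procedure. The documents give no value, so 3 to 7 is assumed (about 2% to 5% of 146). Let S be the true unassisted rate with all failures counted. This is also not given, so 30%, 50% and 70% are assumed.

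**If scored as free.** Overstatement = k/N.
- Per subject: 1/146 = 0.7 point.
- N = 146: 3/146 = 2.1 points; 7/146 = 4.8 points.
- N = 158: 3/158 = 1.9 points; 7/158 = 4.4 points.

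**If censored in Kaplan-Meier.** Let F be the number of all failures among 146. Assume these losses make up a constant share k/F of the hazard over time. The estimate becomes S^((F − k)/F).
- At S = 50%, F = 73. For k = 3: 0.50^(70/73) = 51.4%, or +1.4 points. For k = 7: 0.50^(66/73) = 53.4%, or +3.4 points.

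| Assumed true rate | F | k = 3, censored | k = 7, censored |
|---|---|---|---|
| 30% (44/146 = 30.1%) | 102 | +1.1 | +2.6 |
| 50% (73/146) | 73 | +1.4 | +3.4 |
| 70% (102/146 = 69.9%) | 44 | +1.7 | +4.1 |

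Censoring makes the bias smaller but leaves it upward.

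**Scale.** Expected cumulative patency of 84.6% means about 124 of 146 grafts in use at 6 months and 146 − 124 = 22 lost from all causes. Three to seven is 3/22 = 14% to 7/22 = 32% of those. The upper end would need nearly a third of all losses to occur without thrombosis and without any earlier patency procedure.

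**The case against.** A reader might infer that such grafts will be scored as successes and that the reported rate is therefore overstated. The documents do not support that as a flat statement, for three reasons.
- The overstatement arises only if at least one graft is lost without earlier thrombosis or a patency procedure. No rate for this is given, and nothing in the documents anchors 2% to 5%.
- Scoring as success is the literal reading but not the only one open. No estimator is named and abandonment can end follow-up, so an analyst could censor instead.
- Protocol 21.0 speaks of a date on which patency is lost when a serious adverse event leads to abandonment, and does not confine this to cumulative patency. That gives some basis for coding these subjects as no longer patent.

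The weight is also limited. SAP 4.4 states that for secondary endpoints "there are no formal hypotheses that are tested or associated significance levels assigned to results", and that nominal intervals are not for labelling. The losses are not hidden: each is a failure in the primary endpoint, and infection requiring treatment, significant bleeding and pseudoaneurysm are tabulated as serious adverse events. The number and type of interventions is a separate endpoint, so the amount of intervention need not be inferred from the gap between the two rates. That unassisted patency should be nested within cumulative patency is a convention that no section states.

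All of this reduces the size and certainty of the point. None of it supplies the missing rule. The Protocol 21.0 remark does not amend the two-event definition, SAP 4.9 is written for the primary endpoint, and censoring still biases the rate upward.

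**Conclusion.** The gap in the definition is real and is not repaired elsewhere in either document. Under the literal wording, a graft removed or abandoned without earlier thrombosis or a patency procedure is free of failure on unassisted patency, or at best censored, while it fails cumulative patency. Whether this distorts the result depends on whether such losses occur. If they do, the bias is upward: 0.7 point per subject on 146, so 2.1 to 4.8 points for an assumed 3 to 7 subjects (1.9 to 4.4 on 158), or about 1.4 to 3.4 points if censored at an assumed true rate of 50%. The number of losses and the true rate are both assumptions, and the censoring figures also assume a constant share of the hazard.

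The primary test, the sample size of 146 and the type I error are unaffected. The point concerns a descriptive secondary endpoint and is worth fixing because the fix is cheap.

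**What to change.** In Protocol 8.0 and SAP 2.2.2, add a third failure event to primary unassisted patency: loss of access or abandonment of the study graft for any reason, dated to its occurrence. In SAP 4.4 and Protocol 18.0 (Secondary Endpoints), state that the rate is estimated by Kaplan-Meier, with the same censoring rules for death and withdrawal as the primary endpoint.

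The cost is one clause in each definition and one sentence in each analysis section. No new data are needed, because SAP 4.9 already requires the time of loss of access for the primary endpoint. The reported unassisted patency may be slightly less favourable.

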2.2.3 Safety Considerations

All AEs and SAEs will be documented and reported.

2.2.3.1 Clinical Events

Adverse Event (AE) is defined as any undesirable sign, symptom or medical or psychological condition even if the event is not considered to be related or possibly related to the study device or study procedure/intervention. Medical condition/diseases present before starting the study will be considered adverse events only if they worsen after starting study treatment. An adverse event is also any undesirable and unintended effect of research occurring in human subjects as a result of the collection of identifiable private information under the research. Adverse events also include any problems associated with the use of a study device that adversely affects the rights, safety or welfare of subjects.

Serious Adverse Event (SAE) is defined as any undesirable sign, symptom, or medical condition which is fatal, is life-threatening, requires or prolongs in-patient hospitalization, results in persistent or significant disability/incapacity, constitutes a congenital anomaly or birth defect, is medically significant and which the investigator regards as serious based on appropriate medical judgment. An important medical event is any AE that may not result in death, be life-threatening, or require hospitalization but may be considered an SAE when, based upon appropriate medical judgment, it may jeopardize the patient and may require medical or surgical intervention to prevent one of the outcomes listed in the definitions of SAEs.

Unanticipated Adverse Event (UAE) is defined as any event or experience that meets all three criteria below:

- Is unexpected in terms of nature, severity or frequency, given the research procedures that are described in the protocol-related documents AND in the characteristics of the subject population being studied
- Related or possibly related to participation in research. This means that there is a reasonable possibility that the incident may have been caused by the procedures involved in the research study.
- The incident suggests that the research placed the patient or others at greater risk of harm than was previously known or recognized OR results in actual harm to the patient or others

The occurrence of AEs, including SAEs and UAEs, will be monitored throughout the study duration. Adverse event information will be collected and reported on designated AE forms, assessed and classified by the principal investigator as serious/not serious. The investigator will also determine the relatedness of the AE to the study device and study procedure according to the following definitions:

- Related (AE is clearly related to the device/procedure);
- Possibly related (AE may be related to the device/procedure);
- Unrelated (AE is clearly not related to the device/procedure).

Review of Adverse Events. SAEs should be reported to the sponsor within 24 hours of occurrence, and to national and local regulatory authorities, in accordance with national and local policies and procedures. In addition, all unanticipated adverse device effects will be evaluated at the time of occurrence and reported to the sponsor within 24 hours.

2.2.3.2 Clinical Events Committee

A Clinical Events Committee (CEC) will provide medical review of SAEs, UAEs, and any deaths that may occur throughout the study. The CEC will be comprised of the Medical Monitor, and the Sponsor's Chief Science Officer, Chief Technology Officer and Director of Clinical Affairs. Details of CEC operations will be defined in a CEC Charter document.

The principal investigator/institution will permit study-related monitoring, audits of IRB/Ethics committee reviews, and regulatory inspections by providing direct access to source data and documents. On-site data monitoring will be performed by Sponsor's study monitors. Any data discrepancies will be resolved and documented by a standardized data query process.

